6.2 System Overview

The NEUWAVE FLEX MC Microwave Ablation System is a fully featured soft tissue ablation system that uses small diameter flexible ablation probes, a single high-powered, gas cooled microwave source operating at 2.45 GHz, a CO₂-based cooling system, and a Power Distribution Module (PDM). Microwave energy is applied to the target tissue via a single flexible ablation probe, heating the tissue to the point of necrosis. The FLEX System received 510(k) clearance as a Class II device (K163118) for ablation (coagulation) of soft-tissue.

The FLEX MC Microwave Ablation System is designed to be used in target ablation. Target ablation involves placing a probe into a substantial target and then ablating for up to several minutes until the target tissue is necrotic.

The FLEX probes are designed for improved navigation. They are French gauge 6 (outer diameter of less than 2mm) and 150cm long. The FLEX probes contain three temperature measurement sensors that help monitor performance and ensure subject and operator safety.

The FLEX probe antenna was designed to produce an ablation zone substantially equivalent to the predicate NEUWAVE™ PR probe, but within a flexible probe shaft. Like the predicate PR probe, the FLEX probes were designed to produce ablations that encompass the tip of the probe while limiting the overall length of the ablation. Testing in ex-vivo liver, lung, and kidney tissue confirmed that the FLEX probes produce ablations that are substantially equivalent to the predicate probes.

A CO₂ based cooling system ensures the non-active portion of the probe does not exceed temperature requirements. The system uses two customer-supplied CO₂ cylinders. The system monitors the pressure of the tanks and heats the tanks to maintain the desired tank pressure. The FLEX System will select which cylinder to initially use based upon tank pressures.

The MONARCH Platform enables electro-mechanical articulation and precise control of a flexible bronchoscope under continuous and direct control by a physician operator. The MONARCH Bronchoscope is the subject interfacing component of the MONARCH Platform. Additional components of the platform are the MONARCH Cart and the MONARCH Tower. The Platform received 510(k) clearance as a Class II device (K211493) for diagnostics and therapeutics. The system has several components that interface to the Tower and Cart including: The Fluidics tubing, MONARCH Control, Electro-Magnetic Field generator, and Reference Electro-Magnetic sensors.

The flexible MONARCH bronchoscope has a working channel and a camera at the tip. The camera provides the operative perspective, an integrated light at the scope tip, and a 2.1mm inner diameter working channel for the passing of tools. The bronchoscope's working channel is used for irrigation, aspiration, and access for working channel instruments. The single-use bronchoscope is cleared via K193534, and the equivalent re-processed single-use bronchoscope is cleared via K203614.

The MONARCH Bronchoscope is a comprised of two collinear and concentric devices, the inner scope, and the outer sheath, both of which possess 4-way steering control. This configuration enables the capability of telescoping, which enhances the bronchoscope stability and access capability.

The inner scope and outer sheath have a distal section capable of achieving articulation in pitch, yaw, and any combination of the two to enable precise control while driving the bronchoscope. Proximally, the inner scope is equipped with a valve to facilitate the insertion and sealing of various ancillary devices, such as a biopsy needle or FLEX probes. Additionally, the proximal section routes irrigation and aspiration to the working channel.

6.3 Identity of Study Products

For this study, medical devices will be used in accordance with manufacturer design specifications, product instructions, and guidelines. All study medical devices are described, below:

- NEUWAVE FLEX MC Microwave Ablation System and Accessories

Sub-products of the above device are listed, below:

- NEUWAVE FLEX Microwave Ablation System and Accessories
 - FLEX Microwave Ablation System
 - FLEX Microwave Ablation Probes
- Auris MONARCH Platform
 - Cart
 - Tower
 - Bronchoscope

6.4 Study Product Accountability

The NEUWAVE FLEX MC Microwave Ablation System and Accessories must be stored in conditions according to its labeling and IFU. It is the responsibility of the Principal Investigator (PI) to ensure that devices are stored correctly at their respective site.

The PI, or responsible person designated by the PI, must account for all study devices throughout and, at the end of, the clinical study. During the course of the study, the study's ablation probes must be stored in a locked or secure access location. An inventory record must be maintained of all devices received, used, or returned during the clinical trial. The PI must allow the Study Monitor access to the secured facility where the study devices are stored to check inventory.

The Sponsor may supply the Auris MONARCH Platform (including accessories), the NEUWAVE FLEX Microwave Ablation System, and the microwave ablation probes to the study sites. Upon receipt, the Investigator, or delegated staff, will complete the following:

- Conduct an inventory.
- Upon confirmation that all materials arrived intact, complete the Study Article Accountability Log.
- Retain a copy of the signed and dated Packing List for Clinical Supplies for the Investigator's records.

The study device inventory must be available for periodic inspection/verification by relevant Sponsor representatives, including monitors, auditors, site inspectors (routine or for-cause), any regulatory health authority, or IRB/EC.

7.0 STUDY VISIT SCHEDULE

The Schedule of Assessments may be found in Table 1 at the end of the Protocol Summary.

7.1 Visit 1 – Screening

The screening assessments may occur over several dates within 30 days prior to Visit 2 (Ablation Day), but screening assessments should not be conducted on Visit 2 (Ablation Day).

Subjects will be selected for microwave ablation based on the pre-procedure assessments and the Investigator's interpretation of the clinical picture. Eligible subjects will be provided with the study information, including the ICF.

The following screening assessments will occur prior to the study procedure:

- Subjects must be given ample time to review, ask questions, and sign the ICF.
- PI will review inclusion/exclusion criteria and determine if the subject is eligible to participate in the study.
- Collect demographic information (age at time of Visit 1, sex, race, ethnicity).
- Review and collect medical and surgical history, radiation history, and smoking status.
- Record all relevant prior medications (taken within 30 days of Visit 2), including but not limited to blood thinning/anticoagulants, antiplatelets, opioids, systemic chemotherapy, systemic steroids, immunotherapies, anti-inflammatories, NSAIDs, antibiotics, and medications used to treat adverse events
- Record all concomitant procedures.
- Collect height and body weight for BMI.
- Collect key vitals: blood pressure, heart rate, and pulse oximetry.
- Evaluate ECOG performance status.
- Obtain PFTs, which include Spirometry (e.g., FEV1, FVC, FEV1/FVC, FEF25-75, Peak Expiratory Flow, and Maximum Ventilation Volume), Diffusion Capacity (DLCO), Total Lung Capacity (TLC), Functional Residual Capacity (FRC), and Residual Volume (RV).
- Laboratory tests. If these tests (based on SOC) were completed within 30 days of Visit 2, they do not need to be repeated at the Screening visit:
 - CBC with differentials.
 - Coagulation tests, including APTT and PT per site's SOC. INR is required.
 - Only for women of childbearing potential, complete a pregnancy test per site SOC (urine or serum).
 - Data for any serum-based tumor markers (e.g., CEA and LDH) or molecular profiling on the tumor tissue will be collected, if done as part of site SOC.
- Complete the Numeric Pain Rating Scale.
- Complete two validated quality of life questionnaires: EORTC QLQ-C30 and the lung-specific QLQ-LC13. These questionnaires should be administered in person, during the study visit. However, they may be administered over the phone, when needed.
- Chest CT to determine tumor details (e.g., size and location). Tumor size must be measured in 3 axes (axial, sagittal, and coronal). Note: Contrast-enhanced imaging is

preferred, but not required.

- Abdomen and pelvis CT. Note: If the subject had an abdomen and pelvis CT taken within 90 days of the visit, it does not need to be repeated during this visit. Contrast-enhanced imaging is preferred, but not required.
- Brain MRI (with or without contrast), per site SOC. Note: A brain MRI image may be included as part of Screening if it was completed within 12 months of the visit.
- Extremity CT or MRI (with or without contrast), per site SOC. Note: An extremity CT or MRI image may be included as part of Screening if it was completed within 90 days of the visit.
- Record any adverse events (AEs) or serious adverse events (SAEs) that may have occurred after the signing of the ICF.

7.2 Visit 2 – Ablation Procedure Through Discharge

Visit 2: Pre-Procedure

INR should be one of the first assessments completed on the ablation day to ensure it is ≤ 1.5 or the ablation should be rescheduled. Other assessments, if completed, do not need to be repeated as long as the ablation is completed within two weeks of the originally scheduled ablation.

- PI will review inclusion/exclusion criteria and determine if the subject continues to be eligible to participate in the study.
- Document any changes or updates to the subject's relevant concomitant medications (blood thinning/anticoagulants, antiplatelets, opioids, systemic chemotherapy, systemic steroids, immunotherapies, anti-inflammatories, NSAIDs, antibiotics, and medications used to treat adverse events)
- Document any changes or updates to the subject's concomitant procedures.
- Collect key vitals: blood pressure, heart rate, and pulse oximetry.
- Evaluate ECOG performance status.
- Laboratory tests:
 - Coagulation tests, including APTT and PT per site's SOC. INR is required.
 - Only for women of childbearing potential, complete a pregnancy test per site SOC (urine or serum).
- Complete the Numeric Pain Rating Scale.
- Record any AEs or SAEs that may have occurred since the last visit.

Visit 2: Intra-Procedure

The Sponsor will provide access to a Product Development Specialist and/or a Medical Specialist experienced in this procedure for the treating physician as needed. Please refer to the User Manual for additional details.

- CBCT to guide the microwave ablation probe to the target tumor(s) and ascertain the location of the probe after the robotic bronchoscope has been retracted. CBCT scans will be used at a minimum of three timepoints pre- and post- the ablation process:
 - (1) Pre-Navigation: Prior to starting navigation, CBCT will be used to confirm general tumor details and tumor segmentation for navigation (i.e., augmented fluoroscopy).
 - (2) Pre-Ablation: Immediately before the ablation, use CBCT to confirm that the probe is in the intended location, and if it is not, reposition the probe.
 - (3) Post-Ablation: After completing the ablation, use CBCT to confirm that the ablation margins are adequate.
- Perform the microwave ablation procedure: Perform an initial ablation for a maximum of 5 minutes, then after waiting for approximately 10 minutes, perform a CBCT scan to ascertain appropriate progression of the size of the ablation zone. This allows for assessment of the ablation zone to determine whether a sufficient margin has been achieved.
 - If adequate minimal margin was not achieved, additional ablations may be performed.
 - If probe repositioning is required, additional CBCT confirmation is required to ensure the probe is in the intended location.
 - Additional ablations should be no more than 5 minutes per ablation.
 - CBCT imaging must be completed after any additional ablation.
- Record ablation procedure details, including but not limited to:
 - Date and time of the ablation procedure.
 - Anatomical location of ablations.
 - Number of ablation cycles, power, and time used for each ablation.
 - Number of CBCT scans performed for probe placement and margin assessment.
 - Total radiation exposure from the procedure.
 - Number of probes used, type of probes, and probe placement attempts per ablation.
 - Duration of procedure, measured as the time when the bronchoscope enters the endotracheal tube to the time when the last CBCT scan is taken.
- Evaluate Technical Success, defined as all A0 and A1 ablation classification determinations (complete tumor ablation with a surrounding minimal margin) as assessed by **CBCT imaging**, immediately following the ablation procedure.
- Record any AEs or SAEs that may have occurred during the procedure.

Visit 2: Post-Procedure – Discharge

- Document any changes or updates to the subject's relevant concomitant medications (blood thinning/anticoagulants, antiplatelets, opioids, systemic chemotherapy, systemic steroids, immunotherapies, anti-inflammatories, NSAIDs, antibiotics, and medications used to treat adverse events).
- Document any changes or updates to the subject's concomitant procedures.
- Complete the Numeric Pain Rating Scale.
- Collect key vitals: blood pressure, heart rate, and pulse oximetry.
- Collect UB-04 data on procedural cost.
- LOS, measured from post-ablation to discharge. Note: after the ablation procedure, the subject will be observed for up to 23 hours before discharge, except in cases where the Investigator deems it is necessary for the subject to remain hospitalized.
- Record any AEs or SAEs that may have occurred after the procedure until the subject is discharged.

7.3 Visit 3 – 30-day Follow-up

Visit 3 occurs 30 days (-7 to +14 days) after the ablation procedure. The subject will visit the study site for the following assessments:

- Document any changes or updates to the subject's relevant concomitant medications (blood thinning/anticoagulants, antiplatelets, opioids, systemic chemotherapy, systemic steroids, immunotherapies, anti-inflammatories, NSAIDs, antibiotics, and medications used to treat adverse events)
- Document any changes or updates to the subject's concomitant procedures.
- Complete two validated quality of life questionnaires: EORTC QLQ-C30 and the lung-specific QLQ-LC13. These questionnaires should be administered in person, during the study visit. However, they may be administered over the phone, when needed.
- Collect key vitals: blood pressure, heart rate, and pulse oximetry.
- Evaluate ECOG performance status.
- Evaluate Technique Efficacy, defined as ablation of the target tumor(s) with the ablation zone completely overlapping or encompassing the entire target tumor(s) using **CT imaging** at 30 days (-7 to +14 days) post the original ablation procedure.
- Record readmission to any hospital for any unplanned reason within 30 days of the ablation. The Investigator will assess the reason for the admission and capture the reason in the clinical database.
- Record any applicable AEs or SAEs:
 - If within 30 days of the ablation procedure, record any AEs or SAEs that may have occurred since the last study visit.
 - If after 30 days of the ablation procedure, record only device- or procedure-related AEs or any SAEs that may have occurred since the last study visit.

7.4 Visit 4 – 3-month Follow-up

Visit 4 occurs 3 months (\pm 2 weeks) after the ablation procedure. The subject will visit the study site for the following assessments:

- Document any changes or updates to the subject's relevant concomitant medications (blood thinning/anticoagulants, antiplatelets, opioids, systemic chemotherapy, systemic steroids, immunotherapies, anti-inflammatories, NSAIDs, antibiotics, and medications used to treat adverse events)
- Document any changes or updates to the subject's concomitant procedures.
- Complete two validated quality of life questionnaires: EORTC QLQ-C30 and the lung-specific QLQ-LC13. These questionnaires should be administered in person, during the study visit. However, they may be administered over the phone, when needed.
- Collect key vitals: blood pressure, heart rate, and pulse oximetry.
- Evaluate ECOG performance status.
- Obtain PFTs, which include Spirometry (e.g., FEV1, FVC, FEV1/FVC, FEF25-75, Peak Expiratory Flow, and Maximum Ventilation Volume), Diffusion Capacity (DLCO), Total Lung Capacity (TLC), Functional Residual Capacity (FRC), and Residual Volume (RV).
- Complete chest CT, abdomen and pelvis CT, brain MRI (if site SOC), and extremity CT or MRI (if site SOC) to determine Tumor Progression. Contrast-enhanced images are preferred but not required. If a site takes a PET scan per SOC, the other images should also be taken, per protocol:
 - Local Tumor Progression (LTP), defined as recurrence of the originally ablated tumor(s) within or abutting the ablation zone using Chest CT and the 30-day post-ablation imaging as the baseline.
 - Regional Tumor Progression includes new or progression of pre-existing tumors that were not previously ablated within either lung using chest CT.
 - Distant Tumor Progression includes new or progression of pre-existing tumors outside of the lung using abdomen and pelvis CT, brain MRI, and extremity CT or MRI.
- Record any applicable AEs or SAEs:
 - Record any AEs or SAEs that may have occurred within 30 days of an ablation or re-ablation procedure.
 - Record only device- or procedure-related AEs or any SAEs that may have occurred after 30 days of an ablation or re-ablation procedure.

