8. Quality of Life questionnaires include the validated European Organization for Research and Treatment of Cancer (EORTC) QLQ-C30 and the lung-specific QLQ-LC13. These questionnaires should be administered in person, during the study visit. However, they may be administered over the phone, when needed, using the Sponsor-provided script.
9. Ablation procedure details include, but are not limited to, the following: date and time of procedure, anatomical location of ablations, number of ablation cycles, time and power used for each ablation, number of cone beam CT scans performed for probe placement and margin assessment, number of probe placement attempts per ablation, type of probe(s) used, type of anesthesia, duration of procedure (the time when the bronchoscope enters the endotracheal tube to the time when the last cone beam CT scan is taken) and radiation exposure from CBCT scans and the entire procedure.
10. Contrast-enhanced is preferred for these CT images (chest, abdomen, and pelvis), but not required.
11. CT scan of the chest is used at Screening to determine tumor details (e.g., size, location, and type, if available). Tumor size must be measured in 3 axes (axial, sagittal, and coronal).
12. CT scan of the chest is used at every follow-up visit to determine tumor details (e.g., size and location) and to assess local tumor control. If PET (positron emission tomography) scan is taken during follow-up as part of SOC, the site must also perform the diagnostic CT as per protocol. Technique Efficacy and Local Tumor Progression will be determined based on image analysis.
13. The abdomen and pelvis CT required at Screening does not have to be repeated if a previous abdomen and pelvis CT was completed within 90 days of the visit.
14. Brain MRI (with or without contrast) is preferred to be completed at requested timepoints (Screening and Visits 4, 5, and 6), but is not required, and should be taken per site SOC. A brain MRI may be included as part of the Screening imaging if it was completed within 12 months of the visit.
15. For patients with an extremity sarcoma, extremity CT or MRI (with or without contrast) is preferred to be completed at requested timepoints (Screening and Visits 4, 5, and 6), but is not required, and should be taken per site SOC. An extremity CT or MRI may be included as part of the Screening imaging if it was completed within 90 days of the visit.

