4.0 STUDY OBJECTIVES AND ENDPOINTS

The primary objective of the study is to evaluate the safety and effectiveness of the NEUWAVE™ FLEX MC Microwave Ablation System and Accessories used in transbronchial ablation procedures for adult subjects with oligometastatic tumors ($\leq 2\text{cm}$) in the lung.

In this study, “target” tumors are defined as lung tumors that are treated with FLEX MC at the index ablation procedure (i.e., Visit 2). A subject may have a maximum of two target tumors. “Non-target” tumors are defined as lung tumors that are treated with FLEX MC during study follow-up after completion of the primary endpoint, Technique Efficacy assessments at Visit 3 (i.e., Visits 3-6). A subject may not have more than three total tumors treated with FLEX MC (including target and non-target tumors).

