4.3 Secondary Endpoints

- Technical Success: All A0 and A1 ablation classification determinations (complete tumor ablation with a surrounding minimal margin) as assessed by cone beam CT imaging, immediately following the ablation procedure.
- Navigational Success: Successful navigation to the targeted peripheral lung tumor(s) as confirmed using cone beam CT (CBCT).
- Local Tumor Progression (LTP): Recurrence of originally ablated target tumor(s) within or abutting the ablation zone using 30-day post-ablation imaging as the baseline. Measuring progression details will be outlined in a separate Imaging Charter.
- Local Tumor Progression Free Survival (LTPFS): Time from the ablation until local tumor(s) progression (LTP) or death, whichever occurs first. Measuring progression details will be outlined in a separate Imaging Charter.

- Progression Free Survival: Time from the original ablation until tumor(s) progression or death, whichever occurs first (includes local, regional, or distant progression). Measuring progression details will be outlined in a separate Imaging Charter.
- Disease (cancer) Specific Survival: Time from the original ablation until death from the treated primary malignancy.
- Overall Survival: Time from the original ablation until subject death (includes death from any cause).
- Repeat Ablation Efficacy Rate: Rate of original tumors that have been re-ablated successfully (i.e., Technical Success of tumors that have been re-ablated/all original tumors that have been re-ablated).
- Change in all available PFTs (pulmonary function tests) from pre-ablation baseline values to values at 3 months, 6 months, and 12 months post-ablation.
- Change in overall health-related quality of life (HRQOL) and sub-scales, including physical functioning and pain domains, per the validated EORTC QLQ-C30 and QLQ-LC13 questionnaires throughout the duration of the study.

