4.5 Central Review Committee

A central review committee of radiologists will independently review all CT scans (and other scans, as applicable) taken throughout the clinical study in an effort to standardize scan assessment and to minimize potential bias of the treating physician. Both the clinical site's radiographic assessment and the central review committee's assessment will be captured within the CRFs and reported within the final Clinical Study Report. The central review assessment for the following key endpoints will be used for the final analysis. The central review committee will analyze uploaded subject images from the site to assess the following key endpoints and data:

Assessment	Visit 1 (Screening)	Visit 2 (Ablation Visit)	Visit 3 (30 days post-ablation)	Visit 4 (3 months post-ablation)	Visit 5 (6 months post-ablation)	Visit 6 (12 months post-ablation)
Tumor size* (smallest and largest diameters)	X					
Ablation zone (smallest and largest diameters)		X				
Smallest minimal ablation margin		X				
Technical Success		X				
Technique Efficacy			X			
Local tumor progression				X	X	X
Other tumor progression (regional or distant)				X	X	X

*Tumor size, as analyzed by the central review committee, will be used for reporting purposes only. The investigator's assessment of tumor size will be used for inclusion/exclusion purposes.

The composition of the committee and details of how the endpoints will be defined will be specified in a separate Imaging Charter, which will be finalized prior to enrolling the first subject.

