6.0 STUDY PROCEDURES

6.1 Procedure Description(s)

Adult subjects with at least one oligometastatic tumor ($\leq 2\text{cm}$) in the lung located in the outer two-thirds and not closer than 1cm to the pleura (including fissures) with colorectal, renal, or sarcoma histology will have transbronchial microwave ablation performed using the MONARCH Platform.

Multidisciplinary Team

With regard to the clinical treatment approach for each patient, this is best assessed and determined by a local (i.e., site) multidisciplinary team (MDT) (aka tumor board) directly caring for the subject. An MDT discussion will be required prior to subject ablation to determine or ensure 1) that all oligometastatic tumors present at Screening are deemed treatable, 2) the manner/timing that all disease sites will be treated, and 3) the appropriateness of subject inclusion in the study. The MDT will include, at a minimum, a medical oncologist, thoracic surgeon or appropriate surgical specialist, and radiation oncologist.

Screening and Planning

A CT scan of the lung is used at Screening to determine tumor details (e.g., size, location, and type, if available). Tumor size must be measured in 3 axes (axial, sagittal, and coronal).

A maximum of two ipsilateral tumors that meet all inclusion and exclusion criteria may be ablated during a single session as part of this protocol. The second tumor may only be ablated if its planned ablation zone does not overlap with the ablation zone of the previously ablated tumor.

If a subject had three oligometastatic tumors that met all inclusion and exclusion criteria, but only two could be treated, per protocol, on the "Ablation Visit", the third, non-target tumor may be ablated at a later study visit. Similarly, if a new, non-target oligometastatic tumor is identified during study follow-up that meets all inclusion and exclusion criteria, it may be ablated. However, only up to three total oligometastatic lung tumors ("target" or "non-target") may be ablated as part of this protocol during the 12-month follow-up period.

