**Time to Event Endpoints:**

Local Tumor Progression Free Survival (LTPFS) is defined as: Time from the ablation until local tumor(s) progression (LTP) or death, whichever occurs first.

Progression Free Survival (PFS) is defined as: Time from the original ablation until tumor(s) progression or death, whichever occurs first (includes local, regional, or distant progression). Specifically: For local tumors, time from the original ablation until tumor(s) progression or death, whichever occurs first. For regional and distant tumors, time from study day 0 or last local therapy (if treated after study initiation) until tumor(s) progression or death, whichever occurs first.

Disease (cancer) Specific Survival (DSS) is defined as: Time from the original ablation until death from the treated primary malignancy.

Overall Survival (OS) is defined as: Time from the original ablation until subject death (includes death from any cause).

Local Tumor Progression Free Survival (LTPFS), Progression Free Survival (PFS), Disease Specific Survival (DSS), and Overall Survival (OS) will be estimated using the Kaplan-Meier method with 95% confidence intervals provided at month 12. The time from the day of the initiation ablation procedure to the specific event will be derived.

Patients who are re-ablated are considered as reaching an event respectively for each of the LTP, LTPFS and PFS event definitions.

Patients without a progression event, as defined above, will be censored by the last contact date (the last date in the study).

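### The 30-day chest CT has no scheduled read for regional progression, so a new lung tumor seen on it and ablated before Visit 4 may drop out of PFS or be dated late

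*Protocol*

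**What the plan says.** **PFS.** Protocol 4.3 defines it as "Time from the original ablation until tumor(s) progression or death, whichever occurs first (includes local, regional, or distant progression"). It is not tied to any visit.

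**Visit 3 imaging.** Table 1 marks a chest CT at Visit 3. Section 7.3 names one imaging assessment: "Evaluate Technique Efficacy, defined as ablation of the target tumor(s) with the ablation zone completely overlapping or encompassing the entire target tumor(s"). Note 12 to Table 1 adds that a "CT scan of the chest is used at every follow-up visit to determine tumor details" and to assess local control; regional progression is not mentioned. In the central-review table of Protocol 4.5, the row "Other tumor progression (regional or distant") is marked at Visits 4, 5 and 6 and blank at Visit 3. The SAP Section 1 table and the Tumor Progression row of Table 1 show the same.

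**Treatment of new tumors.** Protocol 6.1 states that "if a new, non-target oligometastatic tumor is identified during study follow-up that meets all inclusion and exclusion criteria, it may be ablated", up to three lung tumors in total. Section 4.0 defines non-target tumors as "lung tumors that are treated with FLEX MC during study follow-up after completion of the primary endpoint", so this can begin once the Visit 3 assessment is done.

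**What counts as regional progression.** Sections 7.4 to 7.6 all use: "Regional Tumor Progression includes new or progression of pre-existing tumors that were not previously ablated within either lung using chest CT". Local tumor progression (4.3) covers target tumors only.

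**SAP 8.8.2.** One rule turns treatment into an event: "Patients who are re-ablated are considered as reaching an event respectively for each of the LTP, LTPFS and PFS event definitions". Another sentence starts the clock for regional and distant tumors at day 0 or, for a tumor treated after the study began, at its most recent local therapy. Subjects with no event are censored at last contact.

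**The concern.** A new lung metastasis is a core PFS event in this population. Here it can first appear on a scan with no scheduled progression read and be treated with the study device before the first scan that has one. By then it may no longer fit the definition of regional progression. Losing or delaying such an event can only raise the Kaplan-Meier curve, and the events at risk are those treated with the device under study. PFS is one of four endpoints for which SAP Section 5 provides a month-12 95% confidence interval if the primary endpoint succeeds.

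**Working it through.** No figure in the plan depends on this point, so there is none to reproduce. The check has two parts.

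**1. Does the sequence fit, and do the rules catch the event?**

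- Visit 3: day 30 − 7 = 23 to 30 + 14 = 44. Visit 4: 3 months is about day 91, so 91 ± 14 gives about day 77 to 105.
- Interval between the scans: shortest 77 − 44 = 33 days, nominal 91 − 30 = 61, longest 105 − 23 = 82. Ablating a new tumor in between is feasible.
- Local progression rule: does not apply, because the tumor is not a target tumor.
- Regional progression rule: if the qualifier about prior ablation applies to all tumors, the new tumor is excluded at Visit 4. If it applies only to pre-existing tumors, the tumor can still count as new, but is dated at Visit 4.
- Re-ablation rule: Protocol 4.3 and 6.1 use the term for a second ablation of an original or recurrent target tumor. On that sense, a first ablation of a new tumor is not an event. Section 4.2 divides all ablation procedures into the original and any re-ablation. On that sense, it would be.
- SAP clock sentence: it can be read as restarting time after the new tumor is treated, instead of recording its appearance as an event.

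The outcome therefore turns on three ambiguous phrases.

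**2. How large could the effect be?**

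Assumptions: one-year PFS of 58% (95% CI 49% to 67%), the Protocol Section 3.0 figure for image-guided thermal ablation; constant hazard; N = 145; subjects whose event is lost then follow the same hazard.

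- Hazard: h = −ln(0.58) = 0.545 per year.
- Events by day 30: 1 − exp(−0.545 × 30/365) = 4.4%, and 0.044 × 145 is about 6 subjects. With one-year PFS of 67% and 49%, this is 3.2% and 5.7%, about 5 and 8 subjects.
- Events by day 44: 1 − exp(−0.545 × 44/365) = 6.4%, about 9 subjects.
- Rise in month-12 PFS if all these events were lost: F × 0.58/(1 − F), where F is the proportion with an event by that day.
  - Day 30: 0.0438 × 0.58/0.9562 = 2.7 points (2.2 with one-year PFS of 67%, 3.0 with 49%).
  - Day 44: 0.0636 × 0.58/0.9364 = 3.9 points (3.3 and 4.4).
- If a quarter were lost: 2.7/4 = 0.7 and 3.9/4 = 1.0 point. The quarter is an illustration without a source.
- If no event is lost and all are dated at Visit 4, each still falls before month 12, so the month-12 estimate is essentially unchanged. Only the early part of the curve is too high.

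For scale, ignoring censoring, the 95% half-width at 58% is 1.96 × √(0.58 × 0.42/145) = 8.0 points.

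**The case against.** A reader might infer two stronger things, and the documents support neither.

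The first is that the Visit 3 CT is not read at all, or that new tumors on it go unreported. Note 12 uses the scan for tumor details, Protocol 4.5 sends all CT scans to central review, SAP 8.8.2 summarizes new lung tumors after the procedure, and SAP 8.6 summarizes procedures done for disease progression. What is missing is a scheduled assessment of regional progression.

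The second is that a new tumor ablated before Visit 4 certainly escapes PFS. The most natural grammar attaches the qualifier about prior ablation to pre-existing tumors only. The 30-day scan is the baseline for local progression, not for regional, so a tumor absent at Screening can still be new at Visit 4. The broader sense of re-ablation in Section 4.2 would make its ablation an event. The Imaging Charter, to which Protocol 4.3 and 4.5 defer progression details and endpoint definitions, is not among the documents and may settle the matter. This all stands: escape is possible, not certain.

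The size is also open to attack, and rightly. The 58% counts all PFS events. In this trial those include local and distant progression and death, and a new lung tumor must also meet every entry criterion, fit the three-tumor limit and be treated before Visit 4. So 2.7 to 3.9 points is an unrealistic ceiling.

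Finally, Visit 3 has no abdomen and pelvis CT, so starting the full progression assessment at Visit 4 is a coherent choice. That does not explain leaving out the lung read, for which the scan is in hand. Nor does it resolve the competing readings of what counts as an event.

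**Conclusion.** The point holds as a gap in the schedule and an ambiguity in the event definition. A new lung tumor visible at day 23 to 44 may be lost from PFS or have its clock restarted if it is ablated before Visit 4. If it is kept, it is dated about 33 to 82 days late.

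The bias from lost or delayed events is upward and probably small. The documents give no frequency for the sequence. The 2.7 to 3.9 points at month 12 rest on the 58% reference, a constant hazard, and every early event being an ablatable lung tumor that is treated and then lost. The 0.7 to 1 point is only illustrative. PFS carries no hypothesis test (Protocol 10.6). The correction is worth making because it is cheap and removes a bias that favors the device.

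**What to change.** 1. Add a regional (lung) progression read at Visit 3 to Protocol Table 1, the Section 4.5 table and the SAP Section 1 table, using the chest CT already taken.
2. In Protocol 7.4 to 7.6 and SAP 8.8.2, state that any lung tumor not present at Screening is a regional PFS event, dated at the first scan that shows it, whether or not it is later ablated. Tumors present at Screening and planned for later treatment do not count as new.
3. Amend the SAP 8.8.2 sentence on the regional and distant clock so that local therapy does not restart PFS time for a new tumor; otherwise it would contradict item 2. Align the Imaging Charter with all three changes.

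Cost: wording, and one more field in the central read of a scan already obtained and reviewed. No scan, visit or treatment rule changes. The downside is that reported PFS may be slightly lower.
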